MIFE has a rapid onset of action and achieves peak plasma levels within 1 - 2 hrs of oral dosing. Peak plasma levels and bioavailability increase as a function of dose but are not directly proportional to dose. However, plasma concentrations of MIFE metabolites do increase in direct proportion to dose; metabolites have antiglucocorticoid activity and contribute to long-acting drug effects (Pomara et al., 2002). MIFE is effective with once-a-day dosing. The half-life is 40 hrs following a single dose and 84.6 hrs following multiple doses. Following discontinuation of MIFE, plasma levels are detectable for up to 2 weeks (Heikinheimo et al., 2003). For this study, we selected to use the high MIFE dose of 1200mg, based on recent clinical trials for other neuropsychiatric disorders associated with HPA-axis dysfunction, and that 1200 mg MIFE has been safely administered over extended periods (MIFE Investigator Brochure, Corcept Therapeutics). This study only exposes subjects to MIFE for up to 6 days. We are not planning to reduce MIFE dose during such a brief treatment period. If a subject experiences significant medication side-effects or any serious adverse event or if the participant declines to continue medication, then we will discontinue that participant from the study. It

should be noted that inpatient subjects are under continuous nursing observation throughout the CRU stay and thus adverse events can be identified and addressed rapidly. HC subjects will be instructed to call the study doctor if they have any adverse events. Subjects will be randomized to active MIFE and placebo on a 2:1 ratio.

In the proposed study, MIFE will be administered under an IND ([name] 124365). MIFE (300 mg) and matching placebo will be provided by Corcept Therapeutics, Menlo Park, CA. We will overencapsulate the medication and placebo as necessary. The Johns Hopkins Bayview Investigational Drug Services (IDS) will maintain the inventory and dispense the medication. MIFE absorption and elimination are not affected by age, body weight, BMI, race or sex (Mifepristone Investigator Brochure, Corcept Therapeutics).

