rs- fMRI analysis. Motion statistics and artifact frequency will be compared to insure that there are no group differences. If necessary, outlier subjects will be removed to achieve equality, or, if this is not possible, motion covariates will be used in analyses. We will determine connectivity using a priori specified seed voxels derived from two sources. The first is from coordinates from previously published studies (Muller-Oehring et al., 2015), or anatomical regions derived from published probability atlases (Hammers et al., 2003; Amunts et al., 2005). Primary regions of interest (ROIs) include ventral striatum/NAcc, mPFC, and central nucleus of the AM (Repunte-Canonigo et al., 2015). Additional seed regions of interest may be identified from group differences observed in the alcohol cue task described below. Connectivity will be measured using the peak cross-correlation between the seed region and other brain regions. These cross correlation results obtained for each subject can then be used in a second-stage analysis for making population inferences and group comparisons. For example, the correlation between the resting-state time series from NAcc and the time series from all other brain regions can be used to create a NAcc correlation volume for each subject. The differences in these correlation volumes before and after drug treatment can be compared for the placebo and drug groups in order to characterize group-dependent differences in altered NAcc connectivity resulting from GR antagonist treatment. We hypothesize that medication groups will exhibit significant differences relative to the AUD placebo group and that fewer differences in connectivity will be observed between HCs and medication groups than between HCs and the AUD placebo group, ie. drug treatments will tend to normalize connectivity toward patterns seen in HCs. In addition to seed-based analyses, we will perform exploratory analyses of whole brain functional connectivity using independent component analyses. Group comparisons will be performed using methods developed and published by our collaborator, [name] (Calhoun et al., 2001; Calhoun et al., 2004). Most recently, [name] and collaborators (Nebel et al., 2015) have used these methods to identify functional connectivity 'signatures' associated with individual differences in symptom severity in children with autism.

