This study will include two groups of participants – persons with AUD and healthy controls. AUD subjects will have a current DSM 5 alcohol use disorder and will be actively drinking at least 50% above NIAAA recommended guidelines (women >10 drinks/week and men >20 drinks/week) and at least 5 binge drinking episodes in the past 30 days. Recent heavy drinking will be confirmed by PEth blood spot analysis ≥ 50 ng/mL. HC subjects will not meet DSM 5 criteria for AUD and will not be drinking above NIAAA recommended guidelines as confirmed by PEth blood spot analysis < 50 ng/mL. We expect to consent 450 subjects in order to accrue 150 subjects into the study procedures (N=75 for AUD and N=75 healthy controls). Historically, our retention in the CRU has been outstanding, with over 90% of subjects completing the protocol.

Additional Inclusion Criteria for all subjects:

- Nontreatment seeking volunteers;
- 21 – 60 years old;
- English speaking;
- 5th grade literacy to ensure ability to read study assessment instruments;
- no current serious psychiatric or health problems that would contraindicate study participation;
- BMI > 19 and < 40 ; medication dosing is not weight-adjusted. We have restricted the weight range of participants to reduce weight-associated variability;
- For women, negative urine pregnancy test prior to initiating MIFE treatment and agreement to use nonhormonal birth control for 2 weeks following last MIFE dose. A medical record of surgical sterilization or elevated FSH level confirming post-menopausal status is required to document non-childbearing potential;
- No adult seizure history;
- No serious alcohol withdrawal complications in prior alcohol withdrawal episodes;

- Some non-drinking days on 90-day TimeLine Followback Drinking Calendar;
- Study Physician and PI recommendation.

Exclusion criteria for all subjects:

- Women on hormonal birth control, or who are pregnant, nursing or planning pregnancy; women with unexplained vaginal bleeding;
- Current DSM 5 mood, anxiety or psychosis diagnosis or currently treated with psychiatric medication;
- Current substance use disorder except alcohol, marijuana (mild) or tobacco; current illicit drug use other than marijuana;
- History of serious alcohol withdrawal symptoms (e.g., seizures, hallucinations) or history of inpatient, medicated alcohol withdrawal management, and CIWA-Ar score at time of assessment ≥ 12 ;

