- c. Justification and safety information if non-FDA approved drugs without an IND will be administered.

During the alcohol sensitivity session, subjects will drink 3 doses of alcohol intended to bring their terminal BrAL to 0.10 mg/dL. Also, at the conclusion of the AMR session, participants can consume up to 5 standard drinks of their preferred alcohol type/brand, based on the number of alcohol reinforcers earned during the session. Beverages containing more than 7% alcohol are not regulated by the FDA; they are regulated by the Bureau of Alcohol, Tobacco, Firearms and Explosives. These beverages are legally sold to adults.

7. Study Statistics

- a. Primary outcome variables:

- adverse events and side-effects;

- fMRI changes in re-FC and CA across brain regions under GR regulatory control;
- Reduction in TSST-induced alcohol motivation and drinking;
- cardiovascular responses (HR, BP, ECG) during alcohol sensitivity sessions;
- alcohol euphoric and sedating effects during sensitivity sessions using VAS and Adjective Scales.

b. Secondary outcome variables will examine the effects of MIFE on a variety of psychological measures during alcohol abstinence, alcohol sensitivity sessions and outpatient visits. Secondary outcome measures include:

- Craving for alcohol during the inpatient stay, assessed using VAS, PACS, OCDS, and AUQ;
- Alcohol withdrawal symptom severity, assessed using the CIWA-Ar;
- Mood and personality assessments during the inpatient stay (BPRS, BDI, and BAI);
- Alcohol use during the outpatient follow-up, assessed using timeline followback self-report and PEth levels.

c. Statistical plan including sample size justification and interim data analysis.

Primary and secondary outcome variables will undergo data cleansing and Corrective/Preventive Measures based confirmation of accuracy and missing data. We will perform exploratory data analyses initially (stem-leaf displays, box plots, histograms, and Q-Q plots) and, if necessary, appropriate data transformations will be performed.

Power analyses: All power estimates are based on type I error =0.05, Power > 0.8. Specific aims are to compare GR antagonism versus placebo for:

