Aim 1. Changes in rs-FC and CA across key brain regions under GR gene regulatory control. From the data obtained in preliminary fMRI studies (4.1c), we extracted each subject's connectivity measure (r value converted to Fisher Z score) between left NAcc and 6 mm ROI in the right inferior parietal cortex. Mean and SD connectivity measurement of 0.134, .082 were obtained from alcohol subjects and -.058, .062 were obtained for controls. We made the following assumptions: (a) t1 connectivity will be that of Alc mean (.134) for drug and placebo groups; (b) t2 connectivity will not change for placebo group; (c) t2 connectivity for the drug group will normalize by at least one-third toward HC values, ie: $t2(\text{expt group}) = \text{Alc mean} - (\text{Alc mean} - \text{HC mean})/3 = 0.07$; (d) SD for each cell is the pooled SD (.076); (e) the correlation between repeated measurements (t1 and t2) is 0.5. Using these assumptions a partial eta squared of 0.1563 was calculated for the group x time interaction for a repeated measure ANOVA. Using this estimate with GPower3 (Faul et al., 2007) software we calculated that 25 subjects per group will result in 83% power for detecting a significant interaction at $p < .05$.

Cue-induced Activation: Myrick et al (2008) showed that AUD compared with HC subjects showed increased ventral striatal activation to alcoholic beverage pictures relative to neutral beverage pictures, and that treatment with a combination of naltrexone and ondansetron significantly decreased CA activation. Their paper provided mean and SD information for placebo and drug group ventral striatal activation that was used to estimate effect size for the present proposal for the interaction for a repeated measures anova with between group factor of drug treatment (placebo vs drug) and within group measure of time (baseline and after

treatment). Because this study was performed on a 1.5T scanner, the contrast to noise ratio was multiplied by a factor of 1.3, as described by Hoenig et al.,(2005) to accurately reflect scanning at 3T in the present study. These calculations revealed a partial eta squared value of 0.185, assuming that the drugs in the present study produce at least a comparable effect to the naltrexone/ondansetron treatment. Using this estimate with GPower3 (Faul et al., 2007) software we calculated that 25 subjects per group will result in 90% power for detecting a significant interaction at $p < .05$.

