Aim 2. Reduction of alcohol withdrawal symptoms and craving, and improvement in low mood during early alcohol abstinence. Power for this aim was based on Vendruscolo et al (2015) (Fig 2A) in which MIFE effects were examined on VAS craving scores. Our hypotheses test if placebo (size = n) is different from MIFE. Comparing placebo effects (mean=11.5 (SD=2.1) to active drug effects (mean=9.3 (SD=2.2), total sample size required for the proposed aim is 39 (i.e.,20 in each group).

Aim 3. Reduction of stress-induced alcohol motivation and drinking. Power for this aim was based on Vendruscolo et al (2015) (Fig 2B) in which MIFE effects were examined on drinking during an outpatient treatment phase of the study. This calculation is based on between-subject calculation which overestimates the sample size requirement. Comparing placebo effects (mean (SEM) = 38.0 (10.2)) to active drug effects (mean (SD) = 27.5 (10.2)), total sample size required is 32. Using data from our AMR session in which mean number of drinks is 4.33 (sd = 3.17), we are powered to observe a 50% or greater reduction in drinks earned within the session.

Aim 4. Reduction of alcohol reward and sensitivity. Based on our preliminary data (4A1, Aim 3) and a sample of 50 GR antagonist vs 25 placebo subjects, we are powered to detect a difference of 3.0 degrees (3.3%) in peak skin temperature. Further, using data from our current alcohol sensitivity procedure (mean peak VAS total=168 (SD=118); mean peak liking=47.9 (SD=36.9)), we are powered to observe a 45 - 50% or greater reduction in alcohol subjective effects.

Aim 5. Side-effects. Power calculation is based on the assumption that the number of side-effect reports and adverse events follows a Poisson distribution. In preliminary data (Concept Investigator Brochure), an average of 12 events was reported in MIFE treated subjects. We estimate that 22 subjects in each group will give power > 0.8 for this statistical test.

Statistical Analyses: For aims 1 – 4, AUD and HC subjects will be separately grouped.

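### Stating normalization as fewer detected differences from HC disadvantages mifepristone under 2:1 allocation, because the larger arm detects more differences even if the drug is inert

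*Combined protocol and SAP*

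**What the plan says.** Hypothesis 1a (section 2, specific aim 1) is that GR antagonism will bring AUD connectivity and cue activation closer to HC scans. Section 4a, under rs-fMRI analysis, turns this into two predictions for connectivity. The first is that medication groups will differ from AUD placebo. The second is that "fewer differences in connectivity will be observed between HCs and medication groups than between HCs and the AUD placebo group", which the text glosses as meaning that "drug treatments will tend to normalize connectivity toward patterns seen in HCs".

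The allocation is in section 4a, MIFE Administration: "Subjects will be randomized to active MIFE and placebo on a 2:1 ratio". The planned totals are "N=75 for AUD and N=75 healthy controls" (section 5), and the Aim 4 power paragraph in section 7c gives "a sample of 50 GR antagonist vs 25 placebo subjects". The two counts would therefore come from AUD arms of about 50 and 25.

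Two other places deal with the same hypothesis without counting. The Aim 1 power paragraph (section 7c) assumes that "t2 connectivity for the drug group will normalize by at least one-third toward HC values" while placebo does not change, and tests this through the group-by-time interaction. The Aim 1 analysis paragraph names a repeated-measure ANCOVA with drug group, alcohol history and time. It defines no contrast that means closer to HC. Nothing in the document adjusts the counts for arm size or says which HC subjects, who are themselves randomized to drug or placebo, form the reference.

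**The concern.** The number of connections that reach significance against HC reflects two things: how far the arm lies from HC, and how many subjects the arm contains. With arms of 50 and 25 these cannot be separated. An inert drug would be expected to look further from HC than placebo, and a drug that truly closes part of the gap could look no better, or worse. Setting one list of significant contrasts beside another is also not in itself a test of mifepristone against placebo.

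fMRI change is listed as a primary outcome in section 7a, and section 7c says the study should inform the power of a full-size trial. If the count were used as the reading of normalization, real partial normalization could be missed or reversed.

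**Working it through.** **The plan's own figure first.** Aim 1 states 83% power with 25 per group. Its inputs: "Mean and SD connectivity measurement of 0.134, .082 were obtained from alcohol subjects and -.058, .062 were obtained for controls"; one-third normalization, a shift of (0.134 + 0.058)/3 = 0.064; SD 0.076 per cell; correlation 0.5 between scans.
- SD of change = 0.076 × √(2 × (1 − 0.5)) = 0.076, so d = 0.064/0.076 = 0.842.
- Two-sided 0.05, noncentral t, 25 vs 25: 83.1%. From the stated partial eta squared of 0.1563: 84.7%. The stated figure reproduces.
- The same test with the allocated 50 vs 25 has 92% power. The direct comparison gains from the larger arm and is not biased by it.

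**Inputs for the count.** AUD arms of 50 and 25 (sections 4a and 7c); 75 HC (section 5); alpha from "All power estimates are based on type I error =0.05, Power > 0.8", taken as two-sided. The document does not name the HC reference, so three are shown: all 75, the roughly 25 HC placebo subjects, and arm-matched HC (50 and 25). Gaps of 0.3, 0.5 and 0.8 SD are assumptions, not figures from the document.

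**Chance of flagging a truly different connection, inert drug.** Noncentral t with noncentrality d × √(n₁n₂/(n₁+n₂)). For d = 0.5 and 75 HC:
- mifepristone: 0.5 × √(50×75/125) = 0.5 × 5.477 = 2.74, giving 78%
- placebo: 0.5 × √(25×75/100) = 0.5 × 4.330 = 2.17, giving 57%

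| HC reference | 0.3 SD | 0.5 SD | 0.8 SD |
|---|---|---|---|
| All 75 | 37% vs 25% | 78% vs 57% | 99% vs 93% |
| HC placebo, 25 | 23% vs 18% | 52% vs 41% | 90% vs 79% |
| Arm-matched, 50 / 25 | 32% vs 18% | 70% vs 41% | 98% vs 79% |

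(Mifepristone vs placebo.) The direction is the same under each reference. A stricter threshold does not cure it: at alpha 0.001 with 75 HC and 0.5 SD, 27% vs 12%. With no true gap both are 5%.

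**Gap that mifepristone must close to tie.** Setting the noncentralities equal gives 1 − √[(1/50 + 1/h₁)/(1/25 + 1/h₂)], where h₁ and h₂ are the HC numbers in the two comparisons.
- 75 HC: 1 − √(0.03333/0.05333) = 1 − 0.791 = 21%
- 25 HC: 1 − √(0.06/0.08) = 1 − 0.866 = 13%
- Arm-matched: 1 − √(0.04/0.08) = 1 − 0.707 = 29%

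**Counts over many connections.** Assume 100 connections, of which 30 truly differ by 0.5 SD, with 75 HC. Expected counts under an inert drug are 30 × 0.776 + 70 × 0.05 = 26.8 and 30 × 0.573 + 70 × 0.05 = 20.7. Simulation with an assumed between-connection correlation of 0.3 gave:
- inert drug: 26.8 vs 20.6 unadjusted, 15.6 vs 7.5 with false discovery rate control; unadjusted, mifepristone had more differences in about 78% of trials and fewer in about 19%
- true 20% normalization: 21.3 vs 20.7, about equal
- the plan's one-third normalization: 16.9 vs 21.2, with mifepristone lower in only about 68% of trials

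**At the pilot gap.** The gap is 0.192/0.076 = 2.53 SD. One-third normalization leaves 0.128/0.076 = 1.68 SD. Even with the smallest reference (25 HC), the noncentralities are 1.68 × √(50×25/75) = 6.9 for mifepristone and 2.53 × √(25×25/50) = 8.9 for placebo, against a critical value near 2. Both comparisons are significant almost always, so the count cannot show the normalization that the plan assumes.

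**The case against.** The strongest reply is that the sentence is a hypothesis, not a decision rule. It follows a direct prediction against AUD placebo in the same sentence. The power section treats normalization as a mean shift tested by the group-by-time interaction, and the analysis section names an ANCOVA and no counting step. All of this stands, and none of those tests is biased by unequal arms. A reader might infer that 2:1 allocation undermines Aim 1 as a whole, or that the count formally decides Hypothesis 1a. The document supports neither reading.

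A reader might also infer that an inert drug would always show more differences. It would do so in expectation, and only where real gaps of modest size exist. In the simulated example it showed fewer in about one trial in five. The only gap the document supplies, about 2.5 SD, lies where both arms are flagged nearly always. The bias also works against the drug, so it does not create a false claim of normalization.

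What remains is that the count is the one cross-group statement the plan offers of what normalization would look like. The ANCOVA paragraph does not replace it, since a drug-by-time effect shows that connectivity changed but not, unless its sign is read against the AUD-HC gap, that it moved toward HC.

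**Conclusion.** The point holds for the count statement and no further. Read as written, the count has a built-in handicap for mifepristone where true AUD-HC gaps are modest: the drug must close about 13% to 29% of the gap to break even, depending on the HC reference. At gaps as large as the pilot's the count is uninformative. It can therefore hide or reverse real partial normalization.

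The result rests on arms of about 50 and 25, two-sided testing at 0.05, and equal SDs. Attrition that is equal across arms leaves the imbalance as it is. The percentages also depend on the assumed gaps; the direction does not, given a true gap and an inert drug. This is worth correcting before analysis, but it is a correction of wording in a plan whose direct tests remain sound.

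**What to change.** In section 4a (rs-fMRI analysis) and the Aim 1 analysis paragraph, state that Hypothesis 1a is judged, for each a priori seed-ROI pair, by the mifepristone-minus-placebo difference within AUD at scan 2, adjusted for scan 1, with a 95% CI. Sign it so that positive means toward the HC scan 1 (pre-dose) mean, and also express it as a fraction of the scan 1 AUD-HC gap. Under the plan's own assumptions the difference is 0.070 − 0.134 = −0.064. HC lies below AUD, so this becomes +0.064, and the fraction is 0.064/0.192 = one-third.

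The sign has to be written in. Subtracting the HC mean from both scans merely subtracts a constant: the arm coefficient and its standard error do not change, and HC drops out of the test. Using the pre-dose HC scan also settles the reference group, since all HC subjects can contribute before any dosing.

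Keep counts of significant regions as description only, with arm sizes shown beside them.

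The cost is wording and a little more analysis; both scans are already planned in both groups. The fraction is unstable for pairs with a small scan 1 gap, where the signed difference alone should be reported.

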Immediately following the TSST, subjects begin the AMR session. We have successfully developed an alcohol motivated responding (AMR) model using progressive ratio operant conditioning procedures widely used in preclinical laboratories and adapted for human research. At the start of the session, participants receive a primer drink consisting of one-half of a standard drink of their preferred alcohol. Response requirements (i.e., number of mouse clicks) increase with each earned reinforcer over a total of 10 reinforcement opportunities. During each response set, subjects elect to work for their preferred type of alcohol (0.5 standard drink) or money (\$1.00). At baseline and at 10-min intervals during the AMR session, subjects provide a saliva sample for CORT measurement and complete the two-item Tiffany Brief Craving Scale (Tiffany et al., 2000) (How badly would you like an alcoholic drink right now?; Rate your current desire to drink alcohol) on a visual analog scale (VAS) from 0 (not at all) to 10 (extremely). At the end of the 60 min AMR period, participants receive earned drinks and/or vouchers for earned money. AMR sessions last for 60 min or until no response is made for 10 min, whichever comes first. If the session is terminated, subjects do not gain access to alcohol until the end of the 60-min session. The maximum amount of alcohol that can be earned is 5 standard drinks (SD), earned in 10 response sets (0.5 SD each set). Subjects drink their preferred type of alcohol; alcohol volume is standardized to ensure equivalency across subjects for the amount of absolute alcohol that can be earned. Drinking is paced to ensure that subjects cannot exceed 0.5 SD every 5 minutes or the total consumption of all 5 SDs in a 50-minute period. Subjects also are provided their preferred mixer and snacks.

Alcohol Sensitivity Session:

On day 6, AUD subjects will participate in an alcohol sensitivity session to assess subjective and cardiovascular responses to oral alcohol administration after stabilization on MIFE/placebo. On the morning of the procedure, subjects receive a calorie-controlled breakfast and lunch to control for dietary effects on alcohol absorption. We will obtain a blood sample for MIFE plasma level determination prior to the alcohol session.

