Aim 3. AMR variables include: total number of alcohol drinks earned; total number of responses during the 60-minute session; distribution of responses for alcohol versus money; progressive ratio breakpoint for alcohol (maximum completed ratio value); response rate (responses/min) and response latency to compete the ratio for alcohol and money. We also measure alcohol craving using the Tiffany Craving Scale; these data will be summarized using peak score and area under the curve. The normality of the outcome measures will be examined first and two sample t-test, or equivalent non-parametric methods will be used to compare the outcomes between GR antagonist-treated group and placebo-treated group.

Aim 4: Subjective and physiological data will be collected repeatedly during the alcohol sensitivity session. We will test outcome measures between the two groups using mixed-effect linear regression with random intercept. Baseline measures will be examined as potential confounding factors and added to the model if needed. We will summarize the baseline adjusted area under the curve and peak values of the outcome measures and compare between the two groups using repeated measure ANCOVA model.

Aim 5: We use the SAFTEE to collect comprehensive side-effect information. We will construct negative binomial generalized linear regression model with the number of events as the dependent variable and grouping and other covariates as independent variables. The model will give the difference in the logs of expected numbers of side effect events between the two treatment groups. We will then also make comparisons taking into consideration the duration and severity of the side effects, which are both collected in SAFTEE for each reported side effect event. A summary side-effect score will be calculated as the sum of the duration multiplying the severity of each side effect event.

Secondary analyses: Another objective of this study is to generate power estimation for a full-size future clinical trial.

d. Early stopping rules.

Individual subjects will be discontinued from the protocol if they experience a moderate-to-severe adverse reaction to MIFE. They also will be discontinued for repeated rule violations on the CRU. The study will be discontinued if there is a pattern of MIFE-related AEs or SAEs.

8. Risks

a. Medical risks, listing all procedures, their major and minor risks and expected frequency.

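### Section 4a does not say whether craving ratings continue after an AMR session ends early, so the Aim 3 craving AUC may depend on how long a subject kept responding

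*Combined protocol and SAP*

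**What the plan says.** Section 4a, in the part on the TSST and AMR session on day 5, sets the following.

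- **Sampling.** "At baseline and at 10-min intervals during the AMR session, subjects provide a saliva sample for CORT measurement"; the two-item craving scale is completed at the same times.
- **Session length.** "AMR sessions last for 60 min or until no response is made for 10 min, whichever comes first".
- **What counts as responding.** "During each response set, subjects elect to work for their preferred type of alcohol (0.5 standard drink) or money". Response requirements "increase with each earned reinforcer over a total of 10 reinforcement opportunities".
- **After an early end.** "If the session is terminated, subjects do not gain access to alcohol until the end of the 60-min session". Likewise, "At the end of the 60 min AMR period, participants receive earned drinks and/or vouchers for earned money".

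Section 7c, Statistical Analyses, Aim 3 states: "We also measure alcohol craving using the Tiffany Craving Scale; these data will be summarized using peak score and area under the curve". Arms are compared by two-sample t-test or a non-parametric equivalent. The section gives no time window for the AUC, no scaling to minutes observed and no rule for a shortened session. It describes responses as counted over a 60-minute session. It specifies no analysis of the cortisol samples taken during AMR.

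Hypothesis 3a in section 2 names both craving and earned drinks after social stress as quantities the drug should lower.

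**The concern.** An AUC adds up over the time observed. If ratings stop when responding stops, a subject who gives up at 20 minutes has a smaller craving AUC than one who works for the full hour, even if both feel the same craving throughout. How long a subject responds is observed after randomisation and may differ between arms. A difference in craving AUC could then reflect a difference in session length, and a lower AUC on mifepristone would look like support for Hypothesis 3a.

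A peak is the maximum of however many ratings exist, so it too can depend on session length, though less strongly.

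The gap cannot be closed at the analysis stage, because ratings that were never taken cannot be recovered.

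**Working it through.** The plan states no figure on this point, so there is none to reproduce. The check is a comparison of the sections, followed by arithmetic on assumed session lengths.

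**1. What the wording implies.** Section 4a ties sampling to the AMR session and, in the same paragraph, gives that session two possible ends: 60 minutes, or 10 minutes without a response. Taken literally, sampling ends at whichever comes first. The same paragraph also speaks of a 60-minute period and of a 60-minute session that still has an end after responding has been terminated. On that second use of the word, all seven samples would be taken. No sentence settles which applies.

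**2. Number of ratings on the literal reading.** Ratings = 1 + (minutes ÷ 10). A full hour gives 7, 40 minutes gives 5, 20 minutes gives 3, and the shortest possible session of 10 minutes gives 2.

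**3. AUC at constant craving.** AUC = score × minutes. With an assumed score of 5 on the 0–10 scale:

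- 60 minutes: 5 × 60 = 300
- 40 minutes: 5 × 40 = 200
- 20 minutes: 5 × 20 = 100

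**4. Difference between arms.** With the same constant craving in both arms, the ratio of mean AUCs equals the ratio of mean session lengths. The lengths below are assumptions:

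| Active (min) | Placebo (min) | Ratio | AUC on active |
|---|---|---|---|
| 45 | 45 | 45/45 = 1.000 | no difference |
| 40 | 45 | 40/45 = 0.889 | 11% lower |
| 35 | 45 | 35/45 = 0.778 | 22% lower |
| 30 | 45 | 30/45 = 0.667 | 33% lower |
| 45 | 40 | 45/40 = 1.125 | 12.5% higher |

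**5. Effect on the test.** A simulation of 4,000 trials used the 50 versus 25 split given under Aim 4 of the power analysis in section 7c, a two-sided t-test at 0.05, and no drug effect on craving. Its other inputs are assumptions: mean craving 5, between-subject SD 2, within-subject SD 1, no time trend, session length with SD 12 minutes (rounded to 10 and held between 10 and 60), and length independent of craving. Ratings stop when the session ends, except in the last column.

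| Nominal mean length, active vs placebo | Raw AUC rejects | Peak rejects | AUC ÷ minutes rejects | Full 0–60 AUC rejects |
|---|---|---|---|---|
| 45 vs 45 | 5% | 5.0% | 5.1% | 5.3% |
| 40 vs 45 | 16% | 6.0% | 5.7% | 5.7% |
| 35 vs 45 | 48% | 6.0% | 4.8% | 4.9% |
| 30 vs 45 | 85% | 6.4% | 4.7% | 4.9% |

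The Monte Carlo standard error near 5% is √(0.05 × 0.95 / 4,000) = 0.0034, or about 0.3 percentage points. The peak is therefore only slightly inflated here. With craving that rises late in the hour it would be affected more.

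**6. Limit of the time-averaged AUC.** It holds its level in this simulation because craving was flat and unrelated to stopping. The real task follows a stressor and a primer drink, so craving need not be flat. Averages over 0–20 and 0–60 minutes would then describe different periods after stress.

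**The case against.** The strongest reply is that the plan already intends a fixed hour. Section 4a names a 60-minute period, keeps subjects waiting to its end after early termination, and section 7c counts responses over 60 minutes. On that reading every subject gives seven ratings and there is no bias. This is a fair reading, and it rules out saying that the plan prescribes truncated sampling. It does not remove the gap: the sentence that sets session length supports the opposite reading, and staff following it could stop sampling.

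A reader might also infer that the window is set by the Aim 3 outcome itself. The documents do not support that. Responding for money keeps the session open, so a subject who switches away from alcohol does not shorten it. Hypothesis 3a predicts lower craving and fewer earned drinks, not less total responding. Nor does the text say whether the 10-minute rule applies once all 10 response sets are finished. Session length follows responding of any kind, and the direction of any bias is unknown.

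The form of the AUC is also open. Aim 4 uses a baseline-adjusted AUC. If Aim 3 did the same, the constant-score example would give zero at every length. Any change from baseline would still accumulate over observed minutes, so the dependence would be reduced but not removed.

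Finally, AMR craving is a supporting measure. The primary outcome for this aim in section 7a is alcohol motivation and drinking, the power statement rests on drinking and drinks earned, and the inpatient craving measures in section 7b are other scales. Drinks earned and breakpoint are untouched by the timing of craving ratings. This limits the weight of the point, but Hypothesis 3a does name craving.

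**Conclusion.** The point holds as an ambiguity in the sampling rule together with an undefined AUC window. If sampling stops at termination, the raw craving AUC depends on session length, and arms could differ in AUC with no difference in craving. On the assumptions shown, the difference runs from none at equal lengths to about one third at 30 versus 45 minutes, and the false-positive rate from 5% to 85%. These figures illustrate sensitivity and are not forecasts, since the documents contain no session-length data.

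Two stronger conclusions should not be drawn. The craving comparison is not shown to be uninterpretable, because that would require series that are in fact truncated and lengths that differ between arms. No stated cortisol analysis is harmed either, because none is specified for AMR; for saliva this is a question of data collection only.

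The change is worth making before sessions run, because it is cheap and the lost ratings could not be reconstructed.

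**What to change.** In section 4a, state that the craving scale, and for consistency the saliva sample, is collected at baseline and at 10, 20, 30, 40, 50 and 60 minutes in every subject, whether or not responding has stopped.

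In section 7c, Aim 3, define craving AUC and peak over this fixed 0–60 minute window. If a series is still incomplete, report the time-averaged AUC (AUC divided by minutes observed) as a sensitivity analysis only, for the reason given in step 6 of the check.

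The cost is one sentence in each section, plus a few two-item ratings and saliva samples in subjects who stop early. They already wait until 60 minutes for access to alcohol, so the session does not become longer.
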